**Figure 1. Study Design Overview**

### 13. APPENDIX 1. SCHEDULE OF EVENTS

Procedure	Screening or Baseline Visit	Build-Up Dosing (every month until 4000mcg is reached)	Maintenance Study Visits (6, 18, 30, 42 months)	Maintenance Study Visits (12, 24, 36 months)	Desensitization OFC 48+ months	Randomly selected 1-17 week post-avoidance OFC
Medical/Allergy History	X				X	X
Physical Exam	X				X	X
Peak Flow Rate	X	X	X	X	X	X
Targeted H&P		X	X	X		
SLIT administration		X				
Prick Skin Tests	X			X	X	X
Blood draw for peanut-specific Ig measurements	X			X	X	X
Saliva collection for peanut-specific Ig measurements	X			X	X	X
Blood draw for mechanistic studies	X			X	X	X
DBPCFC	X				X	X

## 14. APPENDIX 2. EVALUATION OF ASTHMA

The evaluation of asthma severity will be assessed using the NHLBI classification as described in the table below.

Classification	Symptoms	Nighttime awakenings	Lung Function	Interference with normal activity	Short acting beta-agonist use
Intermittent (Step 1)	1. $\leq 2$ days per week	$\leq 2x$ /month	1. Normal FEV 1 between exacerbations 2. FEV 1 $> 80\%$ predicted 3. FEV 1 /FVC normal*	4. None	5. $\leq 2x$ /month
Mild Persistent (Step 2)	1. $> 2$ days per week but not daily	3-4x /month	1. FEV 1 $\geq 80\%$ predicted 2. FEV 1 /FVC normal*	3. Minor limitation	4. 3-4 x /month
Moderate Persistent (Step 3 or 4)	1. Daily	$> 1x$ /week but not nightly	1. FEV 1 $\geq 60\%$ but $< 80\%$ predicted 2. FEV 1 /FVC reduced 5%*	3. Some limitation	4. $> 1x$ /week but not nightly
Severe Persistent (Step 5 or 6)	1. Throughout the day	Often 7x /week	1. FEV 1 $< 60\%$ predicted 2. FEV 1 /FVC reduced $> 5\%*$	3. Extremely limited	4. Often 7x /week

\*Normal FEV1/FVC: 8-19 yr = 85%; 20-39 yrs = 80%

9.3	Demographics and Other Baseline Characteristics.....	16
10.	EFFICACY ANALYSES	17
10.1	Primary Efficacy Analysis Approach.....	17
10.2	Secondary & Exploratory Efficacy Analysis.....	19
11.	REFERENCES	20
12.	FIGURES.....	21

ABBREVIATIONS

ABBREVIATION	DEFINITION OR DESCRIPTION
AE	Adverse Event
AVG	Average
BMI	Body Mass Index
BOCF	Baseline Observation Carried Forward
CFB	Change from Baseline
CRF	Case Report Form
CSR	Clinical Study Report
DBPCFC	Double Blind Placebo Control Food Challenge
DCSA	Double Censoring Survival Analysis
ED10	Expected Dose predicted to provoke AE in 10% of the population
FDA	Food and Drug Administration
FCSS	Food Challenge Symptom Score
ICH	International Conference on Harmonisation
ICSA	Interval Censoring Survival Analysis
IND	Investigational New Drug
ITT	Intent-to-Treat
LOAEL	Lowest-Observed Adverse Event Dose Level
LOCF	Last Observation Carried Forward
LSMean	Least Squares Mean
MAR	Missing at Random
MCRT	Minimal Clinically Relevant Threshold
MI	Multiple Imputation
MedDRA	Medical Dictionary for Regulatory Activities
MMRM	Mixed Model Repeated Measures
MNAR	Missing Not at Random
NOAEL	No-Observed Adverse Event Dose Level
NRS	Numeric Rating Scale
PCS	Physical Component Score
PMM	Pattern Mixture Model
PROMIS	Patient Reported Outcomes Measurement Information System
REML	Restricted Maximum Likelihood
SAE	Serious Adverse Event
SAP	Statistical Analysis Plan
SD	Standard Deviation
SLIT	Sublingual Immunotherapy
SOC	System Organ Class
SOP	Standard Operating Procedure
SU	Sustained Unresponsiveness
TLC	Tolerance
TLD	Time to Loss of Desensitization

1. BACKGROUND

This Statistical Analysis Plan (SAP) has been written to address the concerns identified in the March 19, 2014 protocol abbreviated Peanut SLIT and Tolerance (UNC IRB#11-2308), which included our proposed primary analysis plan aimed at assessing effectiveness of peanut SLIT to induce clinical tolerance 6 months after its discontinuation.

We recognize the investigating team's concerns regarding the assumption that patients will be able to clear the food challenge administered after 6 months of SLIT discontinuation to demonstrate clinical tolerance. The team believes this assumption is rather optimistic, less supported by prior research and suspects that the current study protocol calls for negligible success rate by the end of 6 months of SLIT discontinuation as most of the subjects would fail for clinical tolerance. Since time to loss of desensitization (TLD) is an important dimension that, in our knowledge, no prior study has investigated, provides clinically valuable information and helps facilitate future study design, this study provides an opportunity and a robust framework to study the same. As a result, the revised protocol analyzes a systematic approach to address this concern. We believe that with few changes in the study design and efficacy analysis plan, the revised protocol will help address new objectives of primary enquiry and will provide greater precision to cater to individual's need.

With 51 total enrollees, we are midway through the study's conduct with 24 subjects clearing 48 months of dose maintenance period and waiting to be administered the 48th month food challenge and to be randomized to the placebo or the treatment arm as per the existing protocol. The revised study design calls for amendments beyond the 48 months' period of dose maintenance to include 48th month food challenge followed by discontinuation of SLIT for all subjects for at most 17 weeks, dissolving the need for a two-arm trial. Subjects will be randomized to weekly observed time points during 17 weeks following the 48th month food challenge when the final food challenge will be administered to assess individual's persistent desensitization also known as sustained unresponsiveness (SU). The structure of this final food challenge will be similar to that of the earlier (48th month) food challenge with similar levels of administered drug doses.

We have incorporated strong steps in the protocol to be implemented during the study's conduct to ensure minimization of bias due to unblinding and of missing data during the off-SLIT period. We have created a provision for patients who fail to show up on their randomized final food challenge to continue to participate in the clinical trial, providing outcome data during regularly scheduled visits. In addition, multiple analysis techniques are included in this SAP to examine the outcomes of interest and the robustness of results.

In summary, the two-fold objectives are to estimate the population level threshold for desensitization and study the TLD given a desensitization dose level and subjects' characteristics. The proposed primary efficacy analyses deal with special cases of interval censored data using parametric and semi/non-parametric methods of estimation that have been carefully chosen to address the primary questions of interest. A detailed discussion of the primary efficacy analysis approach is presented in Section 10.1.

2. OVERVIEW

This Statistical Analysis Plan (SAP) describes the planned analysis and reporting for protocol Peanut SLIT & TLC (IRB#11-2308: Peanut Sublingual Immunotherapy and Induction of Clinical Tolerance in Peanut Allergic Children (TLC)), dated 19 March 2014 (Version 5.0).

The structure and content of this SAP provides sufficient detail to meet the requirements identified by the Food and Drug Administration (FDA) and International Conference on Harmonization (ICH) of Technical Requirements for Registration of Pharmaceuticals for Human Use: Guidance on Statistical Principles in Clinical Trials. All work planned and reported for this SAP will follow internationally accepted guidelines, published by the American Statistical Association and the Royal Statistical Society, for statistical practice.

The planned analysis identified in this SAP may be included in clinical study reports (CSRs), regulatory submissions, or future manuscripts. Also, post-hoc exploratory analysis not necessarily identified in this SAP may be performed to further examine study data. Any post-hoc, or unplanned exploratory analysis performed will be clearly identified as such in the final CSR.

In preparation of this SAP, the following documents were reviewed in addition to the literature references cited in this SAP:

- Clinical Research Protocol Peanut SLIT and Tolerance (TLC) Version 5.0 (March 19, 2014)
- Team Comments Dated June 30, 2015 and follow-up
- International Conference on Harmonization (ICH) Guidance on Statistical Principles for Clinical Trials (E9).

The reader of this SAP is encouraged to also read the clinical protocol, and other identified documents, for details on the planned conduct of this study. Operational aspects related to collection and timing of planned clinical assessments are not repeated in this SAP unless relevant to the planned analysis.

3. STUDY OBJECTIVES AND ENDPOINTS

3.1 Study Objectives

3.1.1 Primary Objectives

The study has two-fold objectives:

First, we aim to estimate distribution of sensitization threshold predicted to provoke reactions in the peanut-allergic population based on the no-observed and lowest-observed adverse effect levels (NOAELs and LOAELs) observed for subjects upon administration of 48th month DBPCFC; specifically, we would like to know the population sensitization threshold, the dose predicted to provoke reactions in X% of the peanut-allergic population.

Second, given the above estimated population sensitization threshold and the administered dose levels that it lies between, we would like to characterize the SU curve with respect to time for

several end points including time for desensitization threshold as assessed by the final DBPCFC to reduce by half of the estimated sensitization threshold, to drop by a level of the administered dose level, to remain above minimal clinically relevant threshold (MCRT) and finally, to maintain threshold constancy. This will give insight to the length of time peanut SLIT regimen is effective in inducing desensitization at the estimated as well as observed dose level predicted to provoke reactions in X% of the peanut-allergic population.

3.1.2 Secondary Objectives

The multifold secondary objectives include:

1. To evaluate the safety of SLIT regimen administered over initial 48 months of the study period.
2. To study the changes in immune parameters over time and compare these changes among subjects who were induced with clinical tolerance vs. those who failed.
3. To evaluate association of baseline characteristics with desensitization as assessed by the 48th month DBPCFC and with loss of desensitization as assessed by the final DBPCFC.

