#### ***Secondary Objectives:***

*Objective #2:* To evaluate the safety of SLIT regimen administered over the study period.

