#### ***Purpose and Expectations:***

Through Objective #2, we will determine the percentage of adverse events (AE) and serious adverse events (SAE) due to peanut SLIT dosing. There will be a particular focus on symptoms that require treatment and/or hospitalization, symptoms that may lead to poorer compliance, and gastrointestinal symptoms suggestive of eosinophilic disease. We expect that SAEs will be extremely rare. We expect AEs to be more common but to be mostly comprised of transient oropharyngeal itching that does not affect compliance. We expect symptoms of GI and eosinophilic disease to be rare as very little peanut is ingested by the GI route with peanut SLIT

*Objective #3:* To study the changes in immune parameters over time and compare these changes among subjects who were successfully desensitized vs. those who failed. Changes coinciding with the loss of desensitization would also be studied.

*Purpose and Expectations:*

Through Objective #3, we will seek to understand the molecular processes by which SLIT affects the immune system through evaluation of immune mechanisms in relationship to clinical findings of desensitization. We will delineate the impact of peanut SLIT on the subsequent cellular and humoral responses to peanut protein: 1) peanut specific IgE, IgG, and IgG4 response, 2) peanut specific basophil activation, 3) mast cell responses through skin prick testing, and 4) specific T-cell cytokine responses and T regulatory cell (TReg) activation. We anticipate that the effect of peanut SLIT will occur by induction of TRegs, conversion of T cells from an allergic (Th2) to a non-allergic (Th1) lymphocyte response (measured by cytokines, antibody levels, and skin prick test size), a change in peanut-specific basophil activation, or through a combination of the above.

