### **2.2.2 Secondary Endpoints**

Secondary efficacy endpoints include:

- Comparative estimates of changes in immune parameters over time among subjects who were induced with clinical desensitization versus those who failed. Changes coinciding with the loss of desensitization would also be studied.
- Incidence of all adverse events and serious adverse events during the study.
- Incidence of all gastrointestinal and possible gastrointestinal eosinophilic adverse events.

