3.2 Study Endpoints

3.2.1 Efficacy Endpoints

The primary efficacy endpoints are:

- An estimate of the dose as assessed by the 48th month DBPCFC, also called population sensitization threshold, predicted to provoke reactions in 5% and 10% of the peanut-allergic population. This will also give population level NOAEL and LOAEL that would define interval of consecutive administered dose levels within which the population sensitization threshold lies.
- Multiplicative or differential change in the population sensitization threshold as assessed by the 48th month DBPCFC with a unit change in covariates.
- An estimate of time to loss of desensitization for the following events:
 - Subject's true sensitivity threshold to reduce by half, also called half-life of sensitivity threshold.
 - Subject's true sensitivity threshold to maintain at the same level of LOAEL.
 - Subject's true sensitivity threshold to drop by at least one level of LOAEL.
 - Subject's true sensitivity threshold to remain at or above MCRT.
- Estimates of the proportion of patients at a fixed time for any of the above events that define loss of desensitization (bullet 2).
- Multiplicative change in hazard of loss of desensitization with a unit change in covariates.

Secondary efficacy endpoints include:

- Comparative estimates of changes in immune parameters over time among subjects who were induced with clinical desensitization versus those who failed.

- Incidence of all serious adverse events (SAEs) during the study.

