3.2.2 Safety Endpoints

Safety is assessed by the monitoring and recording of adverse events (AEs), clinical laboratory tests, vital signs and physical examination findings.

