7. ANALYSIS POPULATIONS

The following analysis populations are planned for this study:

- **Safety Population (SAFETY):** all patients who receive at least 1 dose of investigational product. All safety analyses and demographic/baseline characterization will be performed using this population, analyzed as treated.
- **Intention-To-Treat Population (ITT):** all patients who are randomized for assessment of clinical desensitization and SU. This population is primary for efficacy and all efficacy analyses will be performed using this population.

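### The SAP's safety objective stops at month 48, against the protocol and the SAP's own endpoint, and the protocol's gastrointestinal/eosinophilic event endpoint is missing from the SAP

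*SAP*

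**What the plan says.** **Objective.** Protocol 2.1, Objective #2, reads "To evaluate the safety of SLIT regimen administered over the study period". SAP 3.1.2 reads "To evaluate the safety of SLIT regimen administered over initial 48 months of the study period".

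**Endpoints.** Protocol 2.2.2 lists two safety endpoints among its secondary endpoints: "Incidence of all adverse events and serious adverse events during the study" and "Incidence of all gastrointestinal and possible gastrointestinal eosinophilic adverse events". The explanation under Objective #2 names "gastrointestinal symptoms suggestive of eosinophilic disease" as one of its points of focus. The SAP's secondary list (3.2.1) has one safety item, "Incidence of all serious adverse events (SAEs) during the study". SAP 3.2.2 then adds a general statement: "Safety is assessed by the monitoring and recording of adverse events (AEs), clinical laboratory tests, vital signs and physical examination findings".

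**Population and handling.** SAP 7 defines the Safety Population as "all patients who receive at least 1 dose of investigational product" and assigns all safety analyses to it. SAP 8.1 plans safety tables for that population without saying what they contain. SAP 8.1.2 says that safety endpoints are not censored.

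**Exposure after month 48.** SAP 1 gives 51 enrolled children. SAP 4 says that 24 of them have passed month 48, are waiting for the desensitization challenge and are still dosing daily. Protocol 5.8 describes the same deferral.

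**The concern.** The SAP's 48-month limit is a stated rule, and it differs from the protocol's. It is also the only time window that the SAP attaches to non-serious events: the SAE endpoint has its own window (the whole study), and SAP 3.2.2 has none. An analyst who works from the SAP could reasonably stop the AE tables at month 48.

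The endpoint list matters for a related reason. Under Objective #2 the protocol expects SAEs to be extremely rare and other AEs to be more common. The one safety endpoint for which the SAP's list states an incidence is therefore the one expected to yield the fewest events. The gastrointestinal/eosinophilic endpoint, which the protocol singles out, has no place in the SAP. What is at stake is whether the protocol's safety endpoints are analysed as planned or left to choices made once the data are known.

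**Working it through.** No power or alpha figure is involved. The check is a comparison of the two documents, with simple arithmetic for size.

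**Step 1: side by side.**

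| Item | Protocol | SAP |
|---|---|---|
| Window of the safety objective | Whole study (2.1) | First 48 months (3.1.2) |
| SAE incidence | Whole study (2.2.2) | Whole study (3.2.1) |
| Incidence of all AEs | Whole study (2.2.2) | AEs named in 3.2.2; no incidence measure or period |
| GI and possible eosinophilic AEs | Separate endpoint (2.2.2) and a focus (2.1) | Absent from the text supplied |

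Row 1 conflicts between the documents, and the SAP entries in rows 1 and 2 conflict with each other. Row 3 is shortened in the SAP's list and survives only in general terms. Row 4 is missing.

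**Step 2: does another section fill the gap?** Protocol section 8 refers to the SAP for full detail, and Protocol 8.1.2 describes only a repeated-measures model for continuous endpoints, which does not produce an incidence. The supplied SAP text goes from the efficacy analyses (section 10) to references and figures, with no section on safety analysis. The MedDRA coding in SAP 9.3 is for medical history. Neither document says how AE incidence is to be summarised.

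**Step 3: which population?** The SAE item sits under secondary efficacy endpoints, and SAP 10.2 restricts secondary efficacy analyses to the ITT population, which SAP 7 defines by randomisation. Taken literally, children who stop before randomisation would not count. SAP 7 also sends all safety analyses to the Safety Population, which is clearly the sensible reading, but the placement of the item leaves two answers.

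**Step 4: how much lies beyond month 48?**

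- Children already past month 48 and dosing: 24 / 51 = 0.471, or 47%.
- The SAP's planned duration is about 225 weeks. Check with 52-week years: 48 × 52/12 + 17 = 208 + 17 = 225 weeks. The 17-week off-drug phase is then 17 / 225 = 7.6% of the planned time, all of it after month 48.
- At the protocol's ceiling of 66 months per child: (66 − 48) / 66 = 18 / 66 = 27% of that child's time. This is a maximum, not an expected value.

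**The case against.** The strongest reply is that nothing is lost. SAP 3.2.2 names AEs as safety endpoints with no time limit, the Safety Population has no 48-month cut-off, safety endpoints are not censored, and the SAE endpoint runs for the whole study. On this view one sentence in the objectives is out of step with the rest. The SAP was also written against protocol Version 5.0 of 19 March 2014, which may explain the mismatch.

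Much of this stands, and it rules out several stronger readings:

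- A reader might infer that the SAP's safety endpoint is SAEs only. SAP 3.2.2 shows that it is not.
- A reader might infer that the SAP discards safety data after month 48. No analysis rule does so.
- A reader might count two protocol endpoints as dropped. One is absent; the other keeps its SAE half, and its AE half appears in general form in 3.2.2.
- A reader might use the 66-month ceiling to put a share of total dosing time after month 48. The documents give no observed durations, off-drug time varies from 1 to 17 weeks, and SAP 4 calls the overrun slight.
- A reader might suppose that eosinophilic events are especially likely late in treatment. The documents say nothing about their timing, only that they are expected to be rare.
- A reader might say that final-challenge reactions are wrongly shut out of the objective. Objective #2 is explained in terms of events due to SLIT dosing, and the final challenge is given off SLIT. Those reactions belong more clearly under the whole-study endpoints.

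What the reply does not meet is the conflict itself, the missing gastrointestinal/eosinophilic endpoint, and the absence of any stated incidence summary. The version date does not help either, because the SAP already describes the amended design, including the children dosing past month 48.

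**Conclusion.** The point holds as a conflict and an omission in the SAP. The 48-month limit in SAP 3.1.2 contradicts the protocol's objective and the SAP's own SAE endpoint. The gastrointestinal and possible eosinophilic endpoint is missing, and all-AE incidence has shrunk to a general mention without a summary. The documented size is 24 of 51 children (47%) on drug past month 48 when the SAP was written. That count takes all enrolled children as the denominator, with no allowance for dropout; the final number could be higher, since the protocol asks for at least 48 months of SLIT. The conclusion that the endpoint is missing rests on the SAP text supplied. The primary efficacy analyses are unaffected. This should be corrected before analysis.

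**What to change.** 1. In SAP 3.1.2, replace the 48-month limit with the protocol's wording, "To evaluate the safety of SLIT regimen administered over the study period".
2. Under SAP 3.2.2, restore both protocol safety endpoints: incidence of all AEs and SAEs, and incidence of gastrointestinal and possible gastrointestinal eosinophilic AEs. Move the SAE item there from the secondary efficacy list.
3. State that these are reported in the Safety Population over the whole study. Number and percentage of children with an event would follow the SAP's own convention for categorical data in 8.1.
4. Make on-drug events after month 48 and challenge reactions identifiable in those tables. A finer split by study phase, or rates per child-month, is optional; the protocol asks only for incidence.

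The cost is a few lines of SAP text and a few tables. Protocol section 6 already requires adverse events to be collected throughout the study, and Protocol 5.6 already has challenge reactions scored, so no new data or visits are needed.

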3.2 Study Endpoints

3.2.1 Efficacy Endpoints

The primary efficacy endpoints are:

- An estimate of the dose as assessed by the 48th month DBPCFC, also called population sensitization threshold, predicted to provoke reactions in 5% and 10% of the peanut-allergic population. This will also give population level NOAEL and LOAEL that would define interval of consecutive administered dose levels within which the population sensitization threshold lies.
- Multiplicative or differential change in the population sensitization threshold as assessed by the 48th month DBPCFC with a unit change in covariates.
- An estimate of time to loss of desensitization for the following events:
 - Subject's true sensitivity threshold to reduce by half, also called half-life of sensitivity threshold.
 - Subject's true sensitivity threshold to maintain at the same level of LOAEL.
 - Subject's true sensitivity threshold to drop by at least one level of LOAEL.
 - Subject's true sensitivity threshold to remain at or above MCRT.
- Estimates of the proportion of patients at a fixed time for any of the above events that define loss of desensitization (bullet 2).
- Multiplicative change in hazard of loss of desensitization with a unit change in covariates.

Secondary efficacy endpoints include:

- Comparative estimates of changes in immune parameters over time among subjects who were induced with clinical desensitization versus those who failed.

- Incidence of all serious adverse events (SAEs) during the study.

